The study intervention is texting of health information from 28 weeks gestation or from time of enrollment (24-34 weeks) through one year postnatally. Participants will be block randomized to either Bright By Text or Team2BF. Blocks will be by CenteringPregnancy group for those in this program and in sequential blocks of the same number of participants for those in individual obstetrical care.

Those randomized to Bright By Text begin receiving texts as soon as they sign up, and those randomized to Team2BF begin receiving texts at 28 weeks or at the time of enrollment if after 28 weeks.

Bright By Text sends messages total from the first trimester through eight years postpartum, with 2-4 messages per week about a wide range of maternal and child health topics as outlined on their website; there are in total 8 messages about breastfeeding from the prenatal period to 4 months postpartum. Team 2BF includes 3-4 breastfeeding-supportive messages per time

interval, sent weekly from 28 weeks gestation through delivery, daily through 2 weeks postpartum, weekly from 2 to 10 weeks, and then monthly to one year. Other maternal health topics are not addressed.

We are not able to collect user interactions with the SMS system (were texts read or not, was message link clicked or not) within the TEAM2BF REDCap/Twilio system; Bright By Text does have ability to collect user interactions but there is no plan to collect this information for the research and no ability for the study team to receive or access it. For TEAM2BF, participants can text STOP ALL or STOP SO MANY (to receive only one message per time point [by week prenatally or by day postpartum]) and for Bright By Text, participants can text STOP at any time to discontinue receiving texts. At the point of any unsubscribe, and at the 6 months postpartum time point, the participant will be invited by text to participate in a 10-15 minute interview about their experience The interview will be audio recorded and the transcript destroyed once call notes are verified against the recording.

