| | Breastfeeding Knowledge Quiz (4 | | | | |
| | questions – answers follow) | | | | |
| | Breastfeeding Self-Efficacy Scale (14 | | | | |
| | items) | | | | |
| One week after | Infant Feeding Information-what milk is | 2 minutes | | | |
| delivery (PP) | baby drinking? | | | | |
| One month PP | Infant Feeding Information | 2 minutes | | | |
| Two months PP | Infant Feeding Information | 15 minutes | | | |
| | Breastfeeding Knowledge Quiz | | | | |
| | Breastfeeding Self-Efficacy Scale | | | | |
| | Breastfeeding Social Support Scale (16 | | | | |
| | items) | | | | |
| | Maternal Satisfaction (6 questions) | | | | |
| Three months PP | Infant Feeding Information | 3-4 minutes | | | |
| | Healthy Development (1 question) | | | | |
| | Maternal Satisfaction (6 questions) | | | | |
| Six months PP | Infant Feeding Information | 8-17 minutes | | | |
| | Healthy Development | | | | |
| | Maternal Satisfaction (6 questions) | | | | |
| | Study Thank you Survey | | | | |

Data to be Collected for your study

Outcome Measures

Aim #1 - Acceptability

Receipt of messages measures acceptability because participants can easily end messaging; if at least 90% of Team2BF participants continue receipt this will indicate acceptability of the intervention. This outcome will be enhanced by asking (a) a single 4 point Likert-scaled question

about the helpfulness of the texts for breastfeeding and (b) whether the participant would or would not refer a friend or family member to Team2BF.

Aim #2 – Breastfeeding Outcomes

The main outcome will be exclusive breastfeeding at 2 months because this is a meaningful milestone toward the public health goal of 6 months exclusive breastfeeding. We will assess partial and exclusive breastfeeding at hospital discharge and at 1, 2, 3 and 6 months post delivery using the World Health Organization definitions for exclusive and partial breastfeeding. We will also assess timing of discontinuation of breastfeeding if this occurs.

Aim #3 – Moderators of Breastfeeding Outcomes (Exploratory aim)

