The privacy of participants will be protected. The consent process will occur in a private space or virtually where the potential participant can protect their own privacy. All interventions occur virtually on a personal phone, so participants are not exposed to others.

Potential Benefit to Research Participants

There are no direct benefits guaranteed to participants. Participants may benefit if the TEAM2BF messaging helps them with their breastfeeding and may benefit if Bright By Text

increases their wellness, but this cannot be guaranteed. We hope the information gained will help future women, their families and their health providers with breastfeeding and ultimately reduce racial inequities in breastfeeding.

Withdrawal of Research Participants

All participants can text STOP to unsubscribe at any point and withdraw themselves from the research and from each of the texting programs. A participant would be withdrawn is if there is any abuse of the texting system with receipt of inappropriate or profane messages. Mother participants who deliver prior to 36 weeks (35 and 6/7 weeks or before) will be exited from the study since the postnatal messaging is not tuned for prematurity.

Alternatives to Participation

The alternative to participation is simply not to participate. The research is not a substitute for clinical care.

Costs to Research Participants

There could be a cost for the texting for participants depending on their phone plan. The study team cannot be responsible for these costs.

Research Participant Compensation

At enrollment, at 1 week postpartum and at 1, 2, 3 and 6 months we will give \$25 gift card and a tangible gift (diapers+wipes or onesies).

Provisions to Monitor the Data to Ensure the Safety of Research Participants

The PI and research coordinator will meet at least every other week to review for adherence to protocol, trouble shooting, and any events. We will not convene a DSMB.

Drugs or Devices

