Participants will use their own smartphones for the study. The smartphone is a device but it is not being studied. The text messages are being studied. Given the definition of software as a medical device (The term "Software as a Medical Device" (SaMD) is defined as software intended to be used for one or more medical purposes that perform these purposes without being part of a hardware medical device. Reference- https://www.fda.gov/medical-devices/digitalhealth-center-excellence/software-medical-device-samd), the text messaging does not appear to be SaMD because it is not being used to treat, diagnose, cure, mitigate or manage a condition or disease. There are no drugs involved in this study.

Additional Information

The program that is used for the TEAM2BF texting is currently Twilio via REDCap. Twilio, a third-party web service, allows SMS text messages to be sent via REDCap Links within the messages go to free content – most content is publicly available, and for those PDFs that are not publicly available, we have used a REDCap function called "Dashboard" that permits us to create an URL for each of the PDFs. Bright By Text (https://brightbytext.org/) is commercially available—when signing up, participants provide due date, zip code, language preference (English or Spanish) and phone number to the site. Research surveys will be sent from REDCap for all participants.

Regarding the study title: The CTSC funding submission long title, "A proposed randomized clinical trial of the effectiveness of a new breastfeeding-supportive texting program designed specifically for African-American/Black expectant women, as compared to a national maternal health texting program, on rates of exclusive breastfeeding at 2 months" has been added to both the Protocol and the Supplemental form. Due to the complexity and length of the formal title, we are requesting to retain the shorter title, "TOPS – Texting to Promote Breastfeeding," as the header in the informed consent. The reason for this request is that the population of interest may have low health literacy and may have negative perceptions of very academic descriptors; the study is the same and is described equally by both the short and long titles.

Community-Based Participatory Research – NA

International information – NA

References

- 1. American Academy of Pediatrics Section on Breastfeeding. Breastfeeding and the Use of Human Milk [Policy Statement]. Pediatr 2012; 129: e827–e841. doi:10.1542/peds.2011-3552

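### Abusive messages can get a mother withdrawn from the research after randomisation, and nothing in the plan keeps her outcomes or her place in her assigned arm

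*Combined protocol and SAP*

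**What the plan says.** The section Withdrawal of Research Participants holds three exits. Two matter here.

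- Staff-imposed exit: "A participant would be withdrawn is if there is any abuse of the texting system with receipt of inappropriate or profane messages". It names no arm, does not define the trigger, and does not say what happens to the mother's data.
- Exit by the mother: "All participants can text STOP to unsubscribe at any point and withdraw themselves from the research and from each of the texting programs". One text therefore ends both the messaging and the research.

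The third exit, delivery before 36 weeks, is a separate matter.

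On the two texting systems, Additional Information says: "The program that is used for the TEAM2BF texting is currently Twilio via REDCap". Bright By Text, in contrast, "is commercially available—when signing up, participants provide due date, zip code, language preference" and a phone number, so it is an outside service. Study Procedures says of Bright By Text's user-interaction data that "there is no plan to collect this information for the research and no ability for the study team to receive or access it". Surveys are common to both arms: "Research surveys will be sent from REDCap for all participants".

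Outcome Measures, Aim #1, sets the acceptability criterion: "if at least 90% of Team2BF participants continue receipt this will indicate acceptability of the intervention". Study Hypotheses asks for more than 90%. The Data Analysis Plan compares exclusive breastfeeding at 2 months between the arms with covariate adjustment. It names no analysis population and gives no rule for missing outcomes. Study Design describes the trial as unblinded.

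**The concern.** Being withdrawn under this rule depends on how a mother behaves once the texts have started, and possibly on how she feels about them. Staff who know her arm decide whether a message is bad enough. Exits of this kind can undo the balance that randomisation gives, because those removed may differ from those kept in ways tied to the outcome.

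Two results could be touched. The primary comparison loses a mother whose feeding outcome could still have been collected. The Aim 1 continuation figure could lose a mother whose messaging ended badly, if she is taken out of the denominator. The plan has no statement of analysis as randomised that would prevent either.

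**Working it through.** **1. What the passages establish together.** Texts start only after allocation, so the exit falls after randomisation. The section concerns withdrawal of research participants, so the rule takes her out of the study and not only off the texting list. Neither that section nor the Data Analysis Plan restores her outcomes or her assigned-arm analysis. Routes for reaching her do exist: Study Procedures already allows calls and email, and lists the medical record as a source.

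**2. Arm size (the only planned figure that bears on this).** The documents give no expected number of abuse withdrawals, so there is none to reproduce. The denominator comes from the sample-size paragraph of the Data Analysis Plan: difference 3 points, SD 5%, power 80%, alpha 0.05.

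- One-sided comparison of means: n = 2 × (1.645 + 0.842)² × (0.05/0.03)² = 34.4, so 35 per group, or 36 with the t distribution. This matches the stated 36. A two-sided test would give 44.
- Attrition: 36/(1 − 0.10) = 40 per group, as stated.

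**3. Primary outcome.** Assume N = 40 in an arm, x = 5 exclusively breastfeeding (12.5%, between the planned 11% and 14%), and k withdrawn mothers, all non-exclusive. The shift is x/(N − k) − x/N.

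| k dropped | Rate | Shift |
|---|---|---|
| 0 | 5/40 = 12.5% | – |
| 1 | 5/39 = 12.8% | +0.3 points |
| 2 | 5/38 = 13.2% | +0.7 points |
| 3 | 5/37 = 13.5% | +1.0 points |
| 4 | 5/36 = 13.9% | +1.4 points |

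With 36 in the arm, one such mother moves 5/36 = 13.9% to 5/35 = 14.3%, or +0.4 points. If the one dropped mother was exclusively breastfeeding, 5/40 becomes 4/39 = 10.3%, or −2.2 points. That is the less likely case at rates of 11–14%.

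**4. Aim 1 continuation.** Assume 40 mothers in Team2BF, with s ending all messages by STOP and k withdrawn for abuse. Counted as not continuing: (40 − s − k)/40. Abuse cases dropped: (40 − s − k)/(40 − k).

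| s | k | Counted | Dropped | Conclusion changes? |
|---|---|---|---|---|
| 2 | 1 | 37/40 = 92.5% | 37/39 = 94.9% | No |
| 3 | 1 | 36/40 = 90.0% | 36/39 = 92.3% | Only under more than 90% |
| 3 | 2 | 35/40 = 87.5% | 35/38 = 92.1% | Under both wordings |
| 4 | 1 | 35/40 = 87.5% | 35/39 = 89.7% | No |

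The last column needs an extra assumption: STOP mothers stay in the denominator while abuse cases leave it. The withdrawal section takes both groups out of the research. Treated alike, s = 3 and k = 1 gives either 36/40 = 90.0% or 36/36 = 100%. All values of s and k are assumptions.

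**The case against.** The strongest reply is that this is a rare-event conduct rule and that most of the apparent damage is inferred. Much of that stands.

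- **Unequal operation.** A reader might infer that the rule acts mainly in Team2BF. The documents do not show it. The rule applies to any participant. The statement that there is "no ability for the study team to receive or access it" concerns texts read and links clicked, not replies, and the same sentence says those data cannot be collected for Team2BF either. Control mothers also deal with the study through REDCap surveys, reminder texts and interview invitations. Greater exposure in Team2BF is plausible because its messages run on the study's own system, but no more than that.
- **Inflated continuation.** On the plain wording of Aim #1, a mother cut off from messages no longer receives them and so counts against acceptability. Inflation follows only if she is removed from the denominator, which no text says.
- **Objectors removed.** Nothing links abusive messages to rejection of the breastfeeding content. Mothers who object have STOP ALL and STOP SO MANY, and are then asked why.
- **Frequency.** Background reports that nobody stopped messaging in the earlier Team2BF study, and the documents give no rate of abusive replies. STOP exits and early deliveries may well remove more mothers.

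What survives is narrower. The plan states a rule that removes a randomised mother at the discretion of unblinded staff, and nothing in it recovers her data. A general statement of the analysis population would help, but it would not recover outcomes that the rule had stopped the study from collecting.

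**Conclusion.** The concern holds as a minor design point. The rule is an avoidable, undefined, staff-imposed exit after randomisation, with no provision for continued outcome collection or for analysis in the assigned arm.

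Its expected size is small. The primary outcome moves by about 0.3 points per non-exclusive mother dropped, assuming 5 of 40 exclusively breastfeeding. It is tempting to set one mother's weight, 1/36 = 2.8 points, against the 3-point target. That is the effect of changing a mother's outcome, not of dropping a non-exclusive mother, and it overstates the matter.

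For Aim 1, one or two such mothers could decide the 90% criterion only when stopping is already close to the limit and only if they leave the denominator. The documents support neither a claim that the rule does inflate acceptability nor a claim that it operates against one arm.

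**What to change.** Reword the rule in Withdrawal of Research Participants so that abuse of the texting system may end the text messaging but does not end study participation. State also that:

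- outcome collection continues by phone, email or record review unless the mother withdraws consent;
- she is analysed in the arm to which she was randomised;
- in Team2BF she counts as not continuing for Aim 1;
- such cases are reported by arm;
- the same analysis rule applies to mothers who text STOP.

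The cost is a few sentences, and the contact routes are already in Study Procedures. The downside is that staff may occasionally need another contact route, or record review only, for a difficult participant.
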